**Table 1: Schedule of Activities**

Assessment / Measurement	Baseline	Month 3	Month 6	Month 9	Month 12
Clinical Evaluation	✓	✓	✓	✓	✓
Dietitian / Coordinator Visit	Weekly (Month 0–1), then bi-weekly	✓	✓	✓	✓
Home $\beta$ -Hydroxybutyrate (Finger-Stick Meter)	Ongoing, $\geq 3\times$ per week	Continuous	Continuous	Continuous	Continuous
Serum $\beta$ -Hydroxybutyrate & Metabolic Panel	✓	✓	✓	✓	✓
Inflammatory Biomarkers (hs-CRP, IL-6, etc.)	✓	–	✓	–	✓
Fasting Lipids, HbA1c, Glucose	✓	–	✓	–	✓
Body Weight / BMI	✓	✓	✓	✓	✓
Blood Pressure & Pulse Logs	Continuous (weekly)	Continuous	Continuous	Continuous	Continuous
CT Angiography of Thoracic Aorta	✓	–	✓	–	✓
Adverse Event Review & Safety Labs	✓	✓	✓	✓	✓
Diet Adherence Assessment	✓	✓	✓	✓	✓

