## 2.3 Risks and Benefits

**Risks:** Although a well-formulated ketogenic diet is generally safe for most individuals when properly supervised, potential risks include dehydration, electrolyte imbalances (particularly low sodium, potassium, or magnesium), and transient increases in serum lipids during the early adaptation phase. Some participants may experience gastrointestinal discomfort, fatigue, or headache - collectively known as “keto flu” - during the first few weeks of dietary transition. In rare cases, prolonged ketosis can exacerbate preexisting hepatic or renal dysfunction or cause elevations in uric acid. For patients with cardiovascular disease, monitoring of lipid profiles and metabolic parameters is needed. To minimize these risks, participants in this study will undergo regular laboratory evaluations, receive individualized dietary guidance from the research team and dietitian, and remain under medical supervision.

throughout the intervention period

The research blood draws performed have a minimal risk of pain, bruising or the feeling of lightheadedness at the time of the blood draw.

Patient PHI will be recorded, used and stored during the course of this study, thus there is a potential risk of participant loss of confidentiality. All data will be recorded, stored, and analyzed using hospital computers on the virtual desktop servers in order to minimize the risk of a breach.

**Benefits:** There is a potential benefit that the ketogenic dietary interventions implemented may help delay the need for aortic repair. Patients will continue standard of care CT imaging for monitoring, and all clinical decisions will be made in accordance with the current standard of care.

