# 6.0 Study Interventions

## 6.1 Study Procedures

Participants will initiate a supervised ketogenic diet formulated to provide approximately 70-75% of calories from fat, 20% from protein, and less than 10% from carbohydrates, consistent with protocols successfully used in therapeutic epilepsy trials but adapted for adult cardiovascular patients. Caloric intake will be individualized to maintain stable weight and adequate micronutrient balance. Each participant will receive an orientation session with a registered dietitian, followed by weekly virtual or phone check-ins for the first month and bi-weekly thereafter. Educational materials, individualized meal plans, and recipes will be provided.

To ensure safety and adherence, participants will use a handheld ketone meter (Keto-Mojo) to measure  $\beta$ -hydroxybutyrate levels three times per week via saliva as well as finger-stick blood testing. These readings will be automatically uploaded to a secure, HIPAA-compliant cloud platform monitored by the study team. Serum ketone validation and metabolic panels, including electrolytes, lipid profiles, and liver function tests, will be obtained at baseline and every three months. A study coordinator will review adherence data weekly and contact participants who fall below target ketosis thresholds ( $\geq 0.5 \text{ mmol/L}$ ). Blood pressure logs and medication compliance will be reviewed at each visit to ensure consistent impulse control (see

Table 1).

Imaging assessments will be performed using standard-of-care CTA at baseline, 6, and 12 months. All studies will follow an institutional low-radiation surveillance protocol optimized for chronic dissection. Measurements will include maximal descending thoracic diameter, true and false lumen cross-sectional areas, and extent of thrombosis. Each scan will be reviewed by two blinded imaging readers to minimize measurement bias.

Participants will remain under the care of their treating cardiovascular physicians throughout the study, ensuring continuation of best-practice medical management. Any indication for surgical or endovascular intervention during the trial will be determined by the treating team using standard clinical criteria, and the patient will be considered to have reached the primary study endpoint.

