## 9.0 Data Safety and Monitoring

The study Principal Investigator and Research Patient Coordinator will monitor for any safety concerns on an ongoing basis. Any symptomatic hypotension, electrolyte disturbance, or weight loss exceeding 10% of baseline will prompt protocol review and dietary adjustment by the study team. Should the principal investigator or designee become aware of any breach of confidentiality, or adverse event, the event will be reported according to institutional guidelines as outlined above, in Section 7.0

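### Table 1 schedules adverse-event review only quarterly, so the first planned enquiry on diet comes at about week 13, after the weeks in which the protocol expects the early symptoms

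*Protocol*

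**What the plan says.** **Adverse-event review.** Table 1 of the protocol has a row for "Adverse Event Review & Safety Labs", ticked at baseline and months 3, 6, 9 and 12. Other rows of the same table show more frequent activity. The dietitian and coordinator row reads "Weekly (Month 0–1), then bi-weekly", and home ketone testing and blood-pressure logs are marked as continuous. The notes under the table name only those last two as continuous activities.

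**Expected early symptoms.** Section 2.3 lists fatigue, headache and gastrointestinal symptoms as possible "during the first few weeks of dietary transition".

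**Staff contacts.** Section 6.1 provides an orientation session "followed by weekly virtual or phone check-ins for the first month and bi-weekly thereafter". It gives these check-ins no agenda. It adds: "A study coordinator will review adherence data weekly and contact participants who fall below target ketosis thresholds". Ketone validation and metabolic panels "will be obtained at baseline and every three months". Section 6.1 also says: "Blood pressure logs and medication compliance will be reviewed at each visit".

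**Monitoring and triggers.** Section 7.1 tracks adverse events from the baseline visit to the month 12 visit. Sections 7.2 and 9.0 commit the investigator and coordinator to ongoing monitoring. Section 9.0 also states: "Any symptomatic hypotension, electrolyte disturbance, or weight loss exceeding 10% of baseline will prompt protocol review".

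**The concern.** The structured enquiry is placed away from the period in which the protocol itself expects symptoms. Baseline is taken to precede the diet, so the transition weeks pass without any scheduled question about adverse events, although staff are in touch with participants throughout them.

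Sections 7.1, 7.2 and 9.0 say over what period events are tracked and who monitors, but not when or how participants are asked. Between quarterly visits, what gets recorded depends on what each participant chooses to mention and to whom.

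Safety belongs to the primary objective and, with adherence, appears among the secondary endpoints in Section 3.0. With 15 participants, a few missed or misdated events would visibly change the safety summary. Section 7.1 records only events judged at least possibly related to participation, and that judgement is harder when onset must be reconstructed weeks later. One Section 9.0 trigger, symptomatic hypotension, also requires that someone learns of a symptom; a blood-pressure reading alone does not show one.

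**Working it through.** The protocol states no adverse-event rate, capture rate or delay, so there is no figure of its own to reproduce. The check is calendar arithmetic on the stated schedule, followed by an illustration on assumed values.

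**Inputs**
- Review at baseline and months 3, 6, 9 and 12 (Table 1).
- Contacts weekly in month 1, then bi-weekly, read here as every two weeks (Section 6.1, Table 1).
- Early symptoms in the first few weeks (Section 2.3), taken here as onset in weeks 1 to 4.
- 15 participants (Section 1.0).
- One month = 365.25 / 7 / 12 = 4.35 weeks.

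**Step 1: time to the first scheduled review on diet.** 3 × 4.35 = 13.0 weeks.

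**Step 2: wait from onset to that review** (13.0 minus the onset week).

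| Onset week | Wait (weeks) |
|---|---|
| 1 | 12 |
| 2 | 11 |
| 3 | 10 |
| 4 | 9 |

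**Step 3: contacts already planned.**
- Before month 3: 4 weekly contacts, then (13.0 − 4.35) / 2 = about 4, so about 8.
- Over 12 months: 4.35 + (52.2 − 4.35) / 2 = about 28, against 4 scheduled adverse-event reviews on diet.
- If bi-weekly meant twice a week, there would be more contacts, and the mismatch would be larger.

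**Step 4: gap if events were asked about at these contacts.** The longest interval between enquiries falls from about 13 weeks to 1 week in month 1 and about 2 weeks afterwards.

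**Step 5: what incomplete capture would do (assumed values only).** Let p be the true proportion of participants with an event and q the share still captured at month 3. With n = 15, expected recorded = 15 × p × q, and the probability that none is recorded = (1 − p × q)^15.

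| p | q | True events expected | Recorded expected | P(none recorded) |
|---|---|---|---|---|
| 0.20 | 1.00 | 3.0 | 3.0 | 0.035 |
| 0.20 | 0.50 | 3.0 | 1.5 | 0.206 |
| 0.40 | 1.00 | 6.0 | 6.0 | below 0.001 |
| 0.40 | 0.75 | 6.0 | 4.5 | 0.005 |
| 0.40 | 0.50 | 6.0 | 3.0 | 0.035 |
| 0.40 | 0.25 | 6.0 | 1.5 | 0.206 |

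With q = 1 nothing is lost. The table shows how sensitive a sample of 15 is. It does not estimate what this trial would miss.

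**The case against.** The strongest reply is that the protocol already commits to continuing surveillance. Section 7.1 tracks events over the whole year, and Sections 7.2 and 9.0 give ongoing monitoring to the investigator and coordinator. Table 1 places a dietitian or coordinator visit weekly and then bi-weekly, so a role charged with monitoring is tied to the frequent contacts. A symptom script could be left to the case report forms. Quarterly structured review and ongoing monitoring do not contradict each other.

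Much of this stands, and it rules out three stronger readings that a reader might infer:

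- **That the check-ins exclude adverse events.** Section 6.1 gives them no agenda, and silence is not exclusion. Only the coordinator's weekly data review is described, and it concerns adherence.
- **That safety is under-counted.** This is a risk and not a shown result. Participants may volunteer everything at the contacts in between.
- **That the Section 9.0 triggers will act months late because early symptoms are missed.** The symptoms in Section 2.3 quoted above are not Section 9.0 triggers. For symptomatic hypotension, the 9 to 12 week wait is a worst case in which nothing is mentioned at about eight contacts. Pressure logs are kept weekly, and the visits at which Section 6.1 has them reviewed may include these contacts. Electrolytes and scheduled weight do follow the quarterly timetable, but a checklist would not change that.

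What the reply does not supply is a scheduled enquiry. Table 1 fixes adverse-event review at quarterly visits while marking other rows as weekly, bi-weekly or continuous. The promise of ongoing monitoring therefore rests on no planned question between quarters.

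**Conclusion.** The point holds as a mismatch between the fixed schedule and the monitoring commitment. The first scheduled adverse-event enquiry on diet falls at about week 13, and an event starting in weeks 1 to 4 waits 12 to 9 weeks for it unless it is reported spontaneously. Early or transient events, and symptomatic hypotension, may therefore be under-counted or poorly dated. The size cannot be derived from the document, which gives neither an event rate nor a capture rate.

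The conclusion assumes that baseline precedes the diet, that bi-weekly means every two weeks, and that no unstated enquiry takes place at the check-ins. If one is intended, the remedy is simply to write it into the schedule. The related-only recording rule in Section 7.1 is a separate source of incomplete counts, which this point does not address.

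This is a cheap improvement that should be made. It does not invalidate the design.

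**What to change.** In Table 1 and Section 7.1, add a short fixed adverse-event checklist to every dietitian or coordinator contact already scheduled, weekly in month 1 and bi-weekly afterwards. It should cover the symptoms named in Section 2.3 and symptoms of hypotension, and record the onset date of each.

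In Section 6.1, state whether the visits at which blood-pressure logs are reviewed include these contacts. Table 1 would then match Sections 7.2 and 9.0.

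The cost is a one-page form and slight extra data entry, with no added visits or blood draws. The change does not shorten the quarterly interval for electrolytes or scheduled weight. The response to any event stays with the investigator.

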**Notes:**

- ✓ indicates a scheduled assessment
- Continuous activities (home ketone testing, BP logs) are ongoing throughout the study.
- All CTAs follow low-radiation, contrast-enhanced dissection surveillance protocols.
- Data from serum assays, imaging, and clinical monitoring will be integrated for correlation analyses between ketosis level, inflammation, and aortic remodeling.

## 6.2 Duration of Participation

The duration of active research participation is 12 months. Participants will remain under the care of their treating cardiovascular physicians throughout the study, ensuring continuation of best-practice medical management. Any indication for surgical or endovascular intervention during the trial will be determined by the treating team using standard clinical criteria, and the patient will be considered to have reached the primary study endpoint.

## 7.0 Regulatory and Reporting Requirements

The entities providing oversight of safety and compliance with the protocol require reporting as outlined below.

### 7.1 Unanticipated Problems and Adverse Event Reporting

Adverse events will be tracked from the time of the baseline visit until the 12 Month visit. Only events that are considered at least possibly related to participation in this study will be recorded on the AE case report form.

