## 1.0 Synopsis

Title:	Nutritional Ketosis as a Novel Therapeutic Strategy to Stabilize Chronic Aortic Dissection in Marfan Syndrome
Study Description:	Patients with Marfan syndrome who have chronic or residual aortic dissection remain at ongoing risk for progressive aortic dilation and eventual need for operative repair. Despite advances in antihypertensive therapy and open/endovascular/hybrid techniques, no medical therapy has been shown to slow aortic enlargement once chronic dissection is established. But promising results have been demonstrated in rodent studies utilizing ketogenic dietary interventions. Therefore, this prospective, single-arm, intent-to-treat pilot clinical trial will test the feasibility, safety, and potential efficacy of inducing and maintaining nutritional ketosis in patients with Marfan syndrome and chronic aortic dissection
Objectives:	
Primary Objective:
 
 
To test the feasibility, safety, and potential efficacy of inducing and maintaining nutritional ketosis in patients with Marfan syndrome and chronic aortic dissection (Prior type A dissection with residual distal dissection or Stanford Type B; and a maximal aortic diameter 4.0-5.0 cm).
 
 
Secondary Objective:
 
 
Observation of changes related to aortic dissection and inflammatory markers
 
Patient adherence to ketogenic dietary recommendations
 

Endpoints:	
Primary Endpoint:
 
 
Freedom from aortic intervention at 12 months compared with historical controls.
 
 
Secondary Endpoints:
 
 
Change in aortic diameter
 
Growth rate
 
Systemic inflammatory markers
 
Dietary adherence metrics
 

Study Population:	15 patients- Prospective Cohort 15 patients- Historical Control
Phase:	N/A
Description of Sites / Facilities Enrolling:	Washington University School of Medicine / Barnes-Jewish Hospital

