### 3.0 Objectives and Endpoints

Objectives	Endpoints
Primary	
Test the feasibility, safety, and potential efficacy of inducing and maintaining nutritional ketosis in patients with Marfan syndrome and chronic aortic dissection	Freedom from aortic intervention at 12 months compared with historical controls.
Secondary	
Observation of changes related to aortic dissection and inflammatory markers  Patient adherence to ketogenic dietary recommendations  Explore the mechanistic relationship between circulating ketone levels, systemic inflammation, and aortic remodeling as measured by imaging and biomarker assays	Change in maximal descending thoracic aortic diameter and annualized growth rate Degree of false-lumen thrombosis Correlation between serum $\beta$ -hydroxybutyrate levels and aortic remodeling using finite-element imaging analysis Changes in systemic inflammatory and metabolic biomarkers Overall diet adherence and safety.

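### Section 7.1 keeps events judged unrelated, even serious or fatal ones, off the adverse event form in a single-arm trial whose primary objective includes safety

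*Protocol*

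**What the plan says.** Protocol Section 7.1 sets the observation window first: "Adverse events will be tracked from the time of the baseline visit until the 12 Month visit". The next sentence narrows what is kept: "Only events that are considered at least possibly related to participation in this study will be recorded on the AE case report form". The section does not say who judges relatedness or by what criteria, and it does not exempt serious or fatal events. No other section overrides it.

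The Synopsis describes a "prospective, single-arm, intent-to-treat pilot clinical trial will test the feasibility, safety, and potential efficacy", and Section 3.0 repeats safety in the primary objective: "Test the feasibility, safety, and potential efficacy of inducing and maintaining nutritional ketosis". Safety appears again among the secondary endpoints, without further definition, as "Overall diet adherence and safety". The Synopsis gives the size as "15 patients- Prospective Cohort 15 patients- Historical Control". Section 4.3 takes the historical control from published cohorts and cites one figure, about 20-25% progressing to intervention in the first year. It gives no background adverse event rate.

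Some outcomes are collected whatever their cause. Table 1 schedules clinical evaluation, metabolic panel, weight, and adverse event review with safety labs at all five visits, continuous blood pressure and pulse logs, and CT angiography at baseline and Months 6 and 12. Sections 6.1 and 6.2 count any indication for surgical or endovascular intervention towards the primary endpoint. Section 9.0 attaches a response to "Any symptomatic hypotension, electrolyte disturbance, or weight loss exceeding 10% of baseline", with no relatedness condition.

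**The concern.** The rule uses relatedness to decide whether an event enters the form at all, when it should be an attribute of an event already entered. Every participant has Marfan syndrome and a chronic dissection and takes antihypertensive drugs, so another explanation for a cardiovascular event is nearly always available. There is no concurrent arm and no background event rate against which to check a judgement of unrelated.

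At stake is whether the trial can answer the safety part of its primary objective. A harm of the diet that nobody expected is the kind of event most likely to be put down to the underlying disease. If it is not entered, a later reviewer cannot see a cluster of such events or re-adjudicate them from the adverse event data. No analysis plan can repair this, because the loss occurs at data capture.

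**Working it through.** The protocol states no adverse event rate, no safety threshold and no precision target for safety, so there is no figure to reproduce. The check has two parts: what the rule removes, and an illustration of how much this could matter with 15 participants.

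**1. What the rule removes**

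| Type of event, if judged unrelated | Captured elsewhere under the protocol? |
|---|---|
| Laboratory abnormality, weight loss | Yes: scheduled panels and weights (Table 1) |
| Low blood pressure | Largely: continuous logs (Table 1) |
| New thoracic dissection or growth in a survivor | Should be visible on scheduled CT (Table 1) |
| Indication for aortic intervention | Yes: primary endpoint (Sections 6.1, 6.2) |
| Death or rupture without an indication for intervention | No place specified |
| Hospital admission, arrhythmia, other clinical event | No place specified |

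The gap is the last two rows. A death without an indication for intervention, judged unrelated, would be neither on the adverse event form nor in the primary endpoint as written.

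**2. Direction and possible size**

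Let p be the 12-month all-cause risk of an event and m the share of such events judged at least possibly related. The form then reflects a risk of p × m. Because m cannot exceed 1, an all-cause rate read from the form is too low, or correct only when m = 1. The expected number of participants with a recorded event is 15 × p × m, and the chance that none is recorded is (1 − p × m)^15.

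Inputs: n = 15 (Synopsis). Both p and m are assumptions, because the protocol gives neither.

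| p | m | Expected recorded | Chance of recording none |
|---|---|---|---|
| 10% | 1 | 1.5 | 0.90^15 = 20.6% |
| 10% | 0.75 | 1.13 | 0.925^15 = 31.1% |
| 10% | 0.5 | 0.75 | 0.95^15 = 46.3% |
| 10% | 0.25 | 0.38 | 0.975^15 = 68.4% |
| 20% | 1 | 3.0 | 0.80^15 = 3.5% |
| 20% | 0.75 | 2.25 | 0.85^15 = 8.7% |
| 20% | 0.5 | 1.5 | 0.90^15 = 20.6% |
| 20% | 0.25 | 0.75 | 0.95^15 = 46.3% |

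**3. What one or two missing events do to an upper limit**

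The exact (Clopper-Pearson) upper limit for x events in 15 is the value of p at which the chance of x or fewer events equals 5% (one-sided 95%) or 2.5% (two-sided 95%). For x = 0 it has a closed form: 1 − 0.05^(1/15) = 18.1%, and 1 − 0.025^(1/15) = 21.8%.

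| Events (assumed) | One-sided 95% upper limit | Two-sided 95% upper limit |
|---|---|---|
| 0 of 15 | 18.1% | 21.8% |
| 1 of 15 | 27.9% | 31.9% |
| 2 of 15 | 36.3% | 40.5% |

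Section 10.0 plans proportions with 95% confidence intervals, which are conventionally two-sided. On that reading, going from 0 to 2 events raises the limit by a factor of 40.5 / 21.8 = 1.86. On the one-sided reading the factor is 36.3 / 18.1 = 2.0.

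**The case against.** The best defence is that the filter governs one form only. Much of the harm data is collected on a schedule, the primary endpoint counts aortic intervention whatever its cause, and neither that endpoint nor the feasibility benchmark in Section 10.0 uses the adverse event form. The threshold of possible relatedness is also an inclusive one. All of this stands and limits the scope, but it does not cover the clinical events with no other specified place of record. That events are also said to be tracked does not help, because the protocol does not say where the unrelated ones would be kept.

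Three stronger readings are tempting, and the protocol does not support them.

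- A reader might infer that Section 7.1 contradicts Section 9.0, whose triggers carry no relatedness condition. It does not: 7.1 governs what is entered on a form and 9.0 governs a response, and both can be followed together. The consequence is only that an event may prompt a protocol review and still be absent from the adverse event form.
- A reader might infer that every adverse event rate is biased downwards. Rates from scheduled labs, weights, CT or aortic intervention are unaffected. A rate of related events is a different quantity, understated only where the attribution was wrong.
- A reader might take it as stated that the study team makes the causality call. Section 7.1 names no assessor. Section 7.2 makes the principal investigator and coordinator responsible for monitoring adverse events, so this is a fair inference and no more.

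It can also be argued that listing every minor unrelated complaint in a 15-person dietary pilot is a matter of preference. That is reasonable, and it is why the fix has a minimum version.

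**Conclusion.** The point holds in this form: the protocol fixes a recording rule that lets serious and fatal clinical events judged unrelated go missing from the adverse event form, in a single-arm trial with safety in its primary objective and no background event rate. All-cause rates from that form can only be understated, or correct if nothing is filtered out, and the attribution cannot be re-examined. This is a poor rule stated in the protocol, not a detail left for an analysis plan.

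The direction is certain but the size is not. The figures rest on assumed risks, assumed shares judged related and assumed event counts. The upper limits also set a rate of related events beside an all-cause rate and correspond to no safety criterion in the protocol. They show how sensitive a 15-person safety statement is to one or two missing events, and do not estimate the actual bias. It should be corrected before enrolment, because events not entered at the time cannot be rebuilt reliably.

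**What to change.** Replace the filtering sentence in Section 7.1 with a rule that adverse events from baseline to Month 12 are recorded regardless of attribution, with seriousness, severity and relatedness as separate fields on the form. At minimum this should cover all serious events, deaths, hospital admissions, aortic events and the events listed in Section 9.0. Report all-cause and related rates separately. Relatedness may still decide what is reported to the review board.

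The cost is one change of wording, a revised case report form and a little more data entry for 15 participants, at visits where Table 1 already schedules adverse event review. No treatment or clinical rule changes.
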